#### **4.3.4. Definition of Baseline**

Baseline is defined as the last available assessment prior to the first intake of IP. For the parameters for which the time of assessment was planned to be collected, if for their assessment on the day of first intake the time is missing, their assessment at time point “PREDOSE” (when applicable) will be considered as baseline, otherwise, previous days last available assessment will be selected. For the parameters for which the time of assessment was not planned to be collected, their assessment on the day of first intake of IP will be considered as baseline. For efficacy endpoints, the baseline visit will be defined as [Table 6](#). If multiple values on the same day qualify as last available assessment, the average of these values will be used in the analysis.

For ECG data assessed in triplicate, baseline is defined as the average (stored without rounding) of the combination of the most complete replicated ECG parameter before first intake of IP and at the same time the closest to it, selecting in the following order:

First consider Day 1, predose:

- Select the average of the last available triplicate ECG parameter on that day;
- If there is no triplicate, select the average of the last available duplicate ECG parameter;
- In the absence of triplicates and duplicates the last available single ECG parameter will become baseline.

If baseline is not yet determined, consider the previous day and repeat the above selection (average of last triplicate, average of last duplicate, last single ECG on that day). Repeat the whole process successively for each previous day(s) as needed until baseline is determined.

#### **4.3.5. Selection and Use of Analysis Visit**

Before first administration of IP, only Baseline will be used for the entire statistical analysis. Pre-baseline assessments will only be listed. After first administration of IP, if multiple valid, non-missing assessments exist in an analysis window, records will be chosen based on the following rules if a single value is needed:

- The record closest to the target day for that visit will be selected, or
- If there are 2 records that are equidistant from the nominal day, or more than 1 record (with time known) on the selected day, the latest record will be taken
- If chronological order cannot be determined (e.g., more than 1 record on the same day with time missing), the average of the records will be computed and reported in the analysis

### **4.4. Handling of Data**

#### **4.4.1. Handling of Missing Data**

##### **4.4.1.1. Handling of Missing Date-Time Data**

No imputations will be done in case of missing date (time) fields, nor for the missing parts of partially known date (time) fields.

Assessments with missing date (time) will be omitted from the analysis.

Event-type data (e.g. adverse events, concomitant medications) with missing date (time) will be allocated to analysis periods using a worst-case approach as explained in the respective sections.

For the date of diagnosis of Sjogren's Syndrome disease to allow the computation of the disease duration, if missing month, impute as January (01), if missing day, impute as the first day of the month (01).

##### **4.4.1.2. Handling of Missing Result Data**

No imputation will be done of missing result data unless otherwise specified. That is, an observed case (OC) analysis will be performed. Endpoints analyzed via mixed model for repeated

measures (MMRM) handle missing data via the maximum-likelihood function. The MMRM will be applied only when the number of subjects with non-missing values is more than 30% of the sample size. Following a hypothetical strategy estimand, non-PK data observed more than 7 days after the last dose of IP will not be used for the on-treatment related analysis visits. PK data observed more than 2 days after the last dose of IP will not be used for the on-treatment related analysis visits.

For analyses of binary endpoints, the non-responder imputation (NRI) method will be used for missing value imputation in addition to the observed case (OC) analysis.

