## 1. INTRODUCTION

This statistical analysis plan (SAP) describes the final statistical analyses of study GLPG3970-CL-207. The results of the analysis will be described in the clinical study report (CSR).

Technical details on derivations and mock tables, listings and figures (TLFs) will be presented in a separate document.

The statistical analysis will process and present the results following the International Council for Harmonization (ICH) standards, particularly the ICH-E3, ICH-E6, ICH-E9, ICH-R9 (R1) and ICH-E14 guidelines.

On 26 November 2021, the Safety Monitoring Committee recommended to immediately terminate Study GLPG3970-CL-207 due to a safety signal of liver toxicity. Therefore, the GLPG3970-CL-207 study was prematurely stopped. In view of this, only the primary endpoint and safety analyses will be performed. Results will be presented in an abbreviated CSR. Any provisions no longer applicable following premature study termination are highlighted in grey.

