## 2.6. Sample Size Justification

Up to 30 subjects are planned to be randomized 2:1, i.e. 20 subjects will receive GLPG3970 (400 mg qd) and 10 subjects will receive placebo. In case of drop-outs due to SARS-CoV-2 infection, additional subjects may be randomized on top of the planned sample size. The number of additional subjects randomized will not exceed the number of subjects dropping out of the study in relation to SARS-CoV-2. Randomization of additional subjects will be decided by the sponsor before study lock or related unblinding has occurred.

This sample size provides favorable operating characteristics for the primary efficacy endpoint (i.e. ESSDAI change from baseline at Week 12) in terms of the modified signal detection methodology r. This methodology will be used to provide further insight into the treatment effect of GLPG3970 over placebo, and will support scenario analyses. The posterior distribution of this treatment effect will be estimated, and from this distribution probabilities of reaching at least a certain effect (delta) will be derived, e.g. a range of plausible effect size values going from as high as  $P(\delta \geq -5)$  to as low as  $P(\delta \geq -2)$ . A common standard deviation (SD) of 4 was assumed for both active and placebo arm.

Probability	Reference value	Outcome
0.852	-5	Signal detected
0.041		No conclusion
0.107		Signal not detected
0.427	-3	Signal detected
0.088		No conclusion
0.485		Signal not detected
0.205	-2	Signal detected
0.050		No conclusion
0.745		Signal not detected

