### 6.2.1. Level of Significance

Statistical tests for efficacy analysis will be done at a 2-sided significance level of 10%.

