#### 6.2.2.1. Derivation Rules

The binary categorizations of the ESSDAI actual values calculated per visit is defined as follows:

- ESSDAI Responder: Subjects having reduction from baseline  $\geq 3$  points by analysis window

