### **Analysis of Binary Endpoint**

The ESSDAI response will be summarized for the OC and NRI using number and percentages by treatment group. Fisher's exact method will be used to compare the GLPG3970 and placebo based on NRI rates. Fisher's exact p-value and 90% modified Santner-Snell confidence interval of the difference in response rates will be presented (In particular, the modification of Santner-Snell methodology proposed by Chang and Zhang in 1999 will be used (score option)). In addition, 90% Clopper-Pearson confidence interval based on NRI rates for each treatment group will be provided.

A frequency plot over time will be provided for the subjects having reduction ESSDAI  $\geq 3$  points.

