### 6.2.2.3. Decision Making Methodology

The decision making methodology described by Frewer et al (Frewer, Mitchell, Watkins, & Matcham, 2016) will be used to provide further insight into the treatment effect of GLPG3970 over placebo, and will support scenario analyses.

[figure not shown]
The posterior distribution of this treatment effect will be estimated, and from this distribution probabilities of reaching at least a certain effect (delta) will be derived, e.g., a range of plausible effect size values going from as high as  $P(\delta \leq -5)$  to as low as  $P(\delta \leq -2)$ . A common SD of 4 was assumed for both active and placebo arm.

More details about this analysis will be provided in a separate document. This output will be generated for decision making purposes and will not be part of the CSR.

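### If the ESSDAI responder analysis is still run after the early stop, visits lost only to that stop count as non-response, and the planned inference rests on those rates

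*SAP*

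**What the plan says.** SAP 1 reports that the Safety Monitoring Committee recommended immediate termination on 26 November 2021: "Therefore, the GLPG3970-CL-207 study was prematurely stopped". It limits the remaining work to the primary endpoint and safety, and marks provisions that no longer apply with grey shading. The SAP's version history dates it 17 December 2021, after the stop.

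The rule for missing binary data is in SAP 4.4.1.2: "For analyses of binary endpoints, the non-responder imputation (NRI) method will be used for missing value imputation". The same sentence adds that an observed-case analysis will also be done. No separate treatment is given for values missing because the study ended.

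SAP 6.2.2.1 defines the categorisation, "ESSDAI Responder: Subjects having reduction from baseline" of at least 3 points, for each analysis window. Under Analysis of Binary Endpoint in SAP 6.2.2.2, response is tabulated both ways as number and percentage, but "Fisher's exact method will be used to compare the GLPG3970 and placebo based on NRI rates". The 90% Clopper-Pearson intervals per arm are also tied to NRI rates. The exact interval for the difference is presented with the Fisher p-value; the text does not name its basis separately.

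SAP 3 handles early treatment discontinuation for any reason with a hypothetical strategy, for the continuous Week 12 change. SAP 4.4.1.2 carries this out by not using non-PK data from more than 7 days after the last dose for on-treatment visits. No estimand is given for response.

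**The concern.** Non-responder imputation is defensible when a missing value reflects something about the subject, such as stopping for toxicity or lack of effect. A visit that never took place because the whole study was halted says nothing about whether that subject was responding. Someone with a 4-point ESSDAI improvement at Week 8 and no Week 12 visit because of the halt becomes a Week 12 failure.

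The SAP's authors knew of the stop when they finalised the rule. Both arms' response rates would be too low, the difference would be distorted, and the only printed p-value and intervals would carry that distortion. The same event is set aside hypothetically for the continuous ESSDAI change and scored as failure for the binary version of the same score, with no stated reason.

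**Working it through.** **Inputs from the documents.** Planned size: "20 subjects will receive GLPG3970 (400 mg qd) and 10 subjects will receive placebo" (SAP 2.6). Test level: "Statistical tests for efficacy analysis will be done at a 2-sided significance level of 10" percent (SAP 6.2.1). Variability: "A common SD of 4 was assumed for both active and placebo arm" (SAP 6.2.2.3). Effects: "a range of plausible effect size values going from as high as" a difference of -5, down to -2 (same section). Responder cut-off: a reduction of at least 3 points.

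**Inputs assumed.** The documents give no responder rate, no number cut off and no missing share. The rates, the placebo mean change and the missing shares below are illustrations.

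**The plan's own figure.** The only operating characteristics stated are for the continuous endpoint. SE = 4 × √(1/20 + 1/10) = 1.549. The decision levels are not stated. Back-fitted levels were used: signal detected if the probability of a difference of -2 or better is at least 80%, so the estimate must be -3.304 or lower; not detected if the probability of -5 or better is at most 10%, so the estimate is above -3.015. These give 0.863/0.037/0.100 at -5, against the stated 0.852/0.041/0.107. All nine cells agree within 0.02, so the SD and sample sizes are read correctly. There is no stated figure for the binary endpoint to reproduce.

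**Step 1: equal missing shares.** If a share m is missing for reasons unrelated to outcome, the expected NRI rate in an arm is p × (1-m). The difference is then (1-m) × (pA - pP). For an assumed 50% vs 20%:

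- m = 20%: 0.8 × 30 = 24 points
- m = 40%: 0.6 × 30 = 18 points
- m = 60%: 0.4 × 30 = 12 points

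**Step 2: rates built from the plan's SD and effects.** Take change as normal with SD 4, and assume a placebo mean of -1. The placebo rate is Φ((-3+1)/4) = 30.9%. A difference of -5 gives an active rate of Φ((-3+6)/4) = 77.3%, and a difference of -3 gives Φ((-3+4)/4) = 59.9%. Power is for the exact two-sided Fisher test at 10%, by full enumeration. Observed-case sizes are 16:8, 12:6 and 8:4.

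| Effect | m | NRI difference (points) | Power, NRI | Power, observed cases |
|---|---|---|---|---|
| -5 | 0 | 46.5 | 72.5% | 72.5% |
| -5 | 20% | 37.2 | 50.9% | 69.2% |
| -5 | 40% | 27.9 | 31.2% | 43.0% |
| -5 | 60% | 18.6 | 19.1% | 41.9% |
| -3 | 0 | 29.0 | 33.2% | 33.2% |
| -3 | 20% | 23.2 | 22.2% | 32.3% |
| -3 | 40% | 17.4 | 15.1% | 16.8% |
| -3 | 60% | 11.6 | 10.0% | 18.5% |

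Under these assumptions, observed cases keep the expected difference at 46.5 or 29.0 points throughout.

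**Step 3: unequal missing shares (active/placebo).** The difference is pA(1-mA) - pP(1-mP).

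- True 60% vs 30%, missing 50%/20%: 0.30 - 0.24 = 6 points
- Same rates, missing 20%/50%: 0.48 - 0.15 = 33 points
- Same rates, missing 10%/40%: 0.54 - 0.18 = 36 points
- True 40% in both arms, missing 50%/20%: 0.20 - 0.32 = -12 points
- Same rates, missing 20%/50%: 0.32 - 0.20 = +12 points

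**The case against.** The strongest objection is that the analysis may not be run. Response is neither the primary endpoint nor a listed secondary endpoint; it is a categorisation derived from the primary score. Read plainly, SAP 1 could exclude it, and the shading that would show this is lost in the text. Against that, the responder analysis sits under the Primary Efficacy Parameter heading. This objection stands, and the point is therefore conditional.

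Observed-case counts will be shown, and a reader could recompute a Fisher test from them. That also stands. The gap is that no observed-case inference is planned.

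Not every stopped subject is imputed. ESSDAI is collected at the early-discontinuation visit (SAP 2.5, Table 1), and an assessment within 7 days of the last dose can fill the window it falls in. The efficacy window table is not visible here. This reduces the problem without removing it.

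A reader might also infer four stronger things that the documents do not support:

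- **That NRI must pull the difference toward zero.** This needs similar missing shares. A calendar-date stop makes that the expectation under randomisation, but chance imbalance at 20:10 can move the difference either way (step 3).
- **That each cut-off placebo subject moves the placebo rate by 10 points.** With 10 subjects this holds only for one who would have responded. At an assumed 20% response, the expected shift is 0.2 × 10 = 2 points.
- **That the SAP contradicts its own estimand.** The hypothetical strategy is defined for the continuous change only. Using NRI for response is an unexplained difference in approach, not a formal contradiction.
- **That the primary result is biased.** The MMRM does not use NRI.

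**Conclusion.** The point holds conditionally. If the ESSDAI responder analysis is retained, the rule scores visits lost only to the study stop as non-response, and the planned test and per-arm intervals, and by implication the difference interval, rest on those rates.

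With equal missing shares unrelated to outcome, the expected difference shrinks by the factor (1-m): 30 points becomes 24, 18 or 12 at 20%, 40% or 60% missing. In the illustrations, Fisher power on observed cases is higher than under NRI at each of these shares, despite the smaller numbers. With unequal shares, the difference may be understated, overstated or created where none exists.

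The true size cannot be stated, because the documents do not say how many subjects were cut off or how many had a usable early-discontinuation assessment. The issue is confined to the binary analysis and is worth correcting because the correction is cheap.

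**What to change.** First, state in the SAP whether the responder analysis is retained after termination. If it is not, nothing more is needed.

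If it is retained:

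1. Keep NRI for subjects who stopped treatment for their own reasons before the termination, including toxicity.
2. For subjects still on treatment at termination, remove from the denominator any visit that was not done because of the stop and has no usable assessment in its window.
3. Report the Fisher p-value and the 90% intervals on observed cases beside the NRI results.

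The restriction to subjects still on treatment matters. Excluding every visit whose window had not opened at termination would also drop subjects who had already stopped for toxicity, which is a poor choice in a study halted for a liver signal.

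The cost is a short SAP change and one extra table. The downside is smaller denominators, so wider intervals.

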#### **4.4.1.3. Censoring of Time-to-Event Data**

Not applicable.

[figure not shown]
#### **4.4.2. Handling of Values Below or Above a Threshold**

Results of continuous parameters, as well as normal limits of these reported as below (or above) the detection limit will be imputed by the value one precision unit smaller (or larger) than the detection limit itself. In listings, the original value will be presented.

Example: if the database contains the value “<0.04”, then for the descriptive statistics the value “0.03” will be used. The value “>1000” will be imputed by “1001”.

For PK data, values below the limit of quantification will be imputed by 0 for the calculation of descriptive statistics presentation; except for the geometric mean and the geometric coefficient of variation (CV%), where it will be imputed as lower limit of quantification (LLOQ)/2. These values will be listed as “below lower limit of quantification (BLOQ)”.

[REDACTED]:

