#### **4.5.2. Calculation of Descriptive Statistics**

For continuous parameters, descriptive statistics will be presented when  $N \geq 2$ . When  $N = 1$ , the observation will not be shown in tables nor in figures of summary statistics but will only be listed.

Descriptive statistics will include:

- the number of non-missing data points (n);
- the arithmetic mean;
- the standard error (SE) and standard deviation (SD);
- the median, minimum and maximum;
- 90% confidence interval (CI) of the mean (if indicated in the relevant section).
- Some parameters namely estimated glomerular filtration rate (eGFR), C-reactive protein (CRP), [REDACTED] and metabolic parameters (fasted insulin, homeostatic model assessment of insulin resistance (HOMA-IR) and HbA1c) are known to deviate heavily from the normal distribution but follow the log-normal distribution well. For these parameters, the geometric mean (GM), geometric standard deviation (GSD), and geometric standard error (GSE) will be also reported for the summaries by treatment group and visit. GM, GSD and GSE are not applicable for the summaries of the changes from baseline, however GM, GSD and GSE will be reported for the summaries of percent changes from baseline. This will be done by obtaining the mean, SD and SE of  $\log(\text{value}) - \log(\text{baseline})$  and then transforming these statistics back to the 'percent change scale' as  $100 \times \{\text{exponential}(\text{statistic}) - 1\}$ .

For PK data, descriptive statistics will include:

- the number of non-missing observations (n);
- the number of data points above the LLOQ;
- the arithmetic mean;
- SE and SD;
- the median, minimum and maximum;
- the CV%;
- the geometric mean and geometric CV%.

If less than 50% of the subjects have quantifiable values, only the number of subjects with data, number of data points above the LLOQ, the arithmetic mean, median, minimum, and maximum will be presented with the original calculated value. The other descriptive statistics will be listed as “NC” (not calculated).

If the calculated descriptive statistic is BLOQ, then it will be presented as “BLOQ”.

Individual values and descriptive statistics of concentrations and PK parameters will be presented with 3 significant digits.

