## Appendix XI: SAS Code

### Mixed Model for Repeated Measures

The SAS code for MMRM model with unstructured variance-covariance matrix for the primary efficacy endpoint is:

```
PROC SQL data = dataset NOPRINT;
  SELECT mean(AVAL) INTO :b FROM ADXX where paramcd = 'XXX' and fasfl = 'Y'
  and avisit = 'Baseline';
QUIT;
```

For parameters planned to be collected/measured at Week 4, Week 8 and Week 12 the following SAS code will be used:

```
PROC MIXED data = dataset;
  CLASS subjid trt visit ;
  MODEL change = visit*trt bsl*visit/ NOINT DDFM=KenwardRoger;
  REPEATED visit / SUBJECT=subjid TYPE=un;
  LSMEANS visit*trt / cl alpha=0.1 at (bsl) = (&meanbsl. );
  ESTIMATE 'GLPG3970 vs. Placebo: Week 4' avisit*trtp 1 0 0 -1 0 0 /CL ALPHA = 0.1;
  ESTIMATE 'GLPG3970 vs. Placebo: Week 8' avisit*trtp 0 1 0 0 -1 0 /CL ALPHA = 0.1;
  ESTIMATE 'GLPG3970 vs. Placebo: Week 12' avisit*trtp 0 0 1 0 -0 -1 /CL ALPHA = 0.1;
  ESTIMATE 'AUEC GLPG3970' avisit*trtp 4 4 2 0 0 0 bsl*avisit %sysevalf(4*&meanbsl.)
  %sysevalf(4*&meanbsl.)
  %sysevalf(2*&meanbsl.) / divisor = 12 CL ALPHA = 0.1;
  ESTIMATE 'AUEC Placebo' avisit*trtp 0 0 0 4 4 2 bsl*avisit %sysevalf(4*&meanbsl.)
  %sysevalf(4*&meanbsl.)
  %sysevalf(2*&meanbsl.) / divisor = 12 CL ALPHA = 0.1;
  ESTIMATE 'AUEC GLPG3970 vs. Placebo' avisit*trtp 4 4 2 -4 -4 -2 / divisor = 12 CL
  ALPHA = 0.1;
RUN;
```

Code for endpoints measured at Baseline, Week 8 and Week 12:

```
LSMESTIMATE trt*visit
  'GLPG3970 vs Placebo: Week 8' 1 0 -1 0,
  'GLPG3970 vs Placebo: Week 12' 0 1 0 -1;
RUN;
```

For the log transformed parameters the following will be applied:

- In the *PROC SQL*: *AVAL* will be replaced by *log(AVAL)*
- In the *PROC MIXED*:
  - o *Change* will be replaced by *geopchg=log(aval)-log(bsl)*
  - o And *bsl* will be replaced by *log(bsl)*

If the default Newton–Raphson algorithm used by SAS PROC MIXED fails to converge, the following will be tried to avoid lack of convergence while maintaining an unstructured variance:

- A. The Fisher scoring algorithm (via the SCORING option of the PROC MIXED statement) will be used to obtain the initial values of covariance parameters:

*PROC MIXED data = dataset **SCORING=5**;*

...

The rest of the code is the same as the first full proc mixed code provided.

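### The SAP 4.4.2 rule for results below detection can return 0, which has no logarithm for the geometric laboratory summaries in SAP 4.5.2

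*SAP*

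**What the plan says.** SAP 4.4.2 sets one rule for continuous parameters: a result below (or above) the detection limit "will be imputed by the value one precision unit smaller (or larger) than the detection limit itself". Its lower-limit example is an entry of `<0.04`, and "then for the descriptive statistics the value “0.03” will be used". Its upper-limit example turns `>1000` into 1001. Listings keep the original result.

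PK data have their own rule in the same section. Values below quantification become 0 for descriptive statistics, except for the geometric mean and geometric CV, "where it will be imputed as lower limit of quantification (LLOQ)/2". A blacked-out item follows that rule.

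SAP 4.5.2 names eGFR, CRP, a redacted item, fasted insulin, HOMA-IR and HbA1c as parameters that "are known to deviate heavily from the normal distribution but follow the log-normal distribution well". For these, "the geometric mean (GM), geometric standard deviation (GSD), and geometric standard error (GSE) will be also reported" by treatment group and visit. Their percent changes are summarised from the log of the value minus the log of baseline, then transformed back. Appendix XI makes the same replacement for any log-transformed parameter that is modelled.

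SAP Section 1 keeps the primary endpoint and safety analyses after the early termination, and SAP 6.3 places laboratory data within safety.

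**The concern.** The two sections do not fit together. The general rule in 4.4.2 can produce 0, while 4.5.2 takes logs of the same variables. No readable text says what happens to the log of 0 outside PK. The PK exception shows that the difficulty was recognised for one data type and not carried over to the others.

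The results at risk are all at the low end, so losing them is not neutral: the geometric mean rises and the geometric SD shrinks. An affected post-baseline value loses that visit's log-scale record. An affected baseline loses every log change for that subject. SAP 4.4.3 says that all measured values will be used, so such a loss would be unintended.

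The substitute also depends on print format: the same limit gives 0 when printed `<1` and 0.9 when printed `<1.0`.

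**Working it through.** **Inputs.** The substitution rule, its examples and the PK exception are in SAP 4.4.2. The log-scale statistics are in SAP 4.5.2. The HOMA-IR formula, fasting insulin times fasting glucose divided by 405, is in the protocol's Definition of Terms. Planned arms are 20 and 10 (SAP 2.6). Assay limits are not given.

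**Step 1: reproduce the SAP's examples.** Substitute = limit minus (or plus) 10^(-d), where d is the number of printed decimals. For `<0.04`: 0.04 - 0.01 = 0.03. For `>1000`: 1000 + 1 = 1001. Both agree with the SAP.

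**Step 2: apply the rule to other printed limits.**

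| Printed result | SAP substitute | Natural log | Half the limit |
|---|---|---|---|
| `<1` | 0 | undefined | 0.5 |
| `<0.1` | 0 | undefined | 0.05 |
| `<0.01` | 0 | undefined | 0.005 |
| `<1.0` | 0.9 | -0.105 | 0.5 |
| `<0.10` | 0.09 | -2.408 | 0.05 |
| `<0.2` | 0.1 | -2.303 | 0.1 |
| `<0.5` | 0.4 | -0.916 | 0.25 |
| `<2` | 1 | 0 | 1 |

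The rule fails only when the limit is exactly one printed precision unit. Half the limit is always positive.

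**Step 3: follow the zero.** SAS, the software of Appendix XI, returns missing for log(0), and SAP 4.4.1.2 does not impute missing results by default. The record therefore leaves the geometric summary. If HOMA-IR is computed from the substituted insulin, 0 × glucose / 405 = 0, and HOMA-IR is lost on the log scale too.

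**Step 4: illustrate the size.** Assume that log values are normal with mean 0 and SD s, so the true geometric mean is 1. A fraction q lies below the limit, which sits at s × z(q) on the log scale.

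- Results dropped: mean log = s × φ(z(q)) / (1 - q). With q = 0.10, z = -1.2816 and φ = 0.1755, so 0.1755 / 0.9 = 0.195. For s = 1.0 the geometric mean is exp(0.195) = 1.215. For s = 0.8 it is exp(0.156) = 1.17, and for s = 1.2 it is exp(0.234) = 1.26.
- Half the limit: mean log = q × (s × z(q) - ln 2) + s × φ(z(q)). For s = 1.0: 0.1 × (-1.2816 - 0.6931) + 0.1755 = -0.022, and exp(-0.022) = 0.978.

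Simulation gave the same values. It also showed the SD of the logs falling from 1.0 to 0.84 when 10% are dropped. Across q from 5% to 30% and s from 0.8 to 1.2, dropping gives 1.09 to 1.82 times the true geometric mean, and half the limit gives 0.95 to 1.02 times.

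**Step 5: chance of meeting the problem.** If 10% of results were affected, the chance of at least one affected subject at a visit is 1 - 0.9^20 = 0.88 in the larger planned arm and 1 - 0.9^10 = 0.65 in the smaller. Early termination may leave fewer subjects per visit.

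**The case against.** The strongest reply is that the trigger is not shown to occur. No assay limit appears in either document, and the SAP's own example gives 0.03, not 0. SAP 6.3.2.1 presents SI units and tabulates central-laboratory data only. Converted limits may not print as a single 1, and mixed print formats for one limit are not shown. This stands, and it makes the point conditional.

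The exposure is also narrower than the list in 4.5.2 suggests. Protocol 6.2 excludes creatinine clearance below 60 mL/min, and SAP Appendix I grades HbA1c only from above 6.0%, so eGFR and HbA1c will not realistically sit at a detection limit near 0. For HOMA-IR, SAP 6.3.2.2 lists no derived tests, Protocol 8.5.2 does not say who derives it, and the example in 4.4.2 speaks of descriptive statistics. Its exposure is therefore an inference. That a record is dropped follows from SAS behaviour, not from SAP text; software that returned minus infinity would give a geometric mean of 0 instead. The redacted item in 4.4.2 may hold a rule for another data type.

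A reader might infer two stronger things. One is that a real fall on active drug, such as CRP becoming undetectable, would be hidden. It would not: the geometric statistics are additional, and the arithmetic mean, median, minimum and ordinary change from baseline keep the substituted value. The other is that a log-scale mixed model of these laboratory parameters would be corrupted. SAP 6.3 and 6.3.2.9 plan descriptive laboratory summaries only, and no readable text assigns the Appendix XI log model to them.

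What remains is a stated rule that can fail for statistics the SAP requires, beside an exception that already solves the same problem for PK.

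**Conclusion.** The gap is real, conditional and minor. If the laboratory's limit for CRP or fasted insulin prints as one precision unit, the lowest results fall out of the geometric summaries, and HOMA-IR is affected too if it uses the substituted insulin. The upward bias of about 20% with 10% of results below the limit rests on assumed log-normal data, an assumed below-limit fraction and records being dropped as in SAS. It illustrates the mechanism and is not an expected bias for this trial. The effect is confined to supplementary geometric laboratory summaries. The documents do not support reading it as a threat to the ESSDAI analysis, the liver safety tables, arithmetic summaries or listings.

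**What to change.** Extend the PK convention already in SAP 4.4.2. For any non-PK parameter summarised or modelled on the log scale, set results below the limit to half the limit for the log-scale statistics. If HOMA-IR is derived from a below-limit insulin, use half the limit as the insulin value for both the log-scale and the arithmetic HOMA-IR summaries. Keep the current rule for all other arithmetic summaries. Before coding, check the laboratory's printed limits for CRP and insulin; if neither equals one precision unit, the sentence is only a safeguard against zeros.

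The cost is one sentence in the SAP and one derivation line. The small downside is that one record then carries two substitution values, one for arithmetic and one for geometric statistics, as PK records already do.
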